AE: Non serious adverse events BCH: Boston Children's Hospital, Boston BRIEF: Behavioural rating of executive function BSID-III: Bayley scales of infant development, version III CPAP: Continuous positive airway pressure CRF: Case report form CSF: Cerebrospinal fluid DMC: Data monitoring committee ECG: Electrocardiograph ESPY: Experimental Delayed Alternation and Spatial Reversal Tasks FLACC: Behavioural scale for scoring postoperative pain in young children measured in 5 areas: face, legs, activity, cry, consolability GA: General anaesthesia GABA: Gamma amino butyric acid HR: Heart rate IV: Intra venous IVH: Intra ventricular haemorrhage NDNMB: Non-depolarizing neuromuscular blocking agent NEPSY: Developmental neuropsychological assessment NIBP: Non invasive blood pressure NICU: Neonatal Intensive Care Unit or Neonatal unit NMDA: n-methyl-d-aspartic acid PACU: Post anaesthesia care unit - also known as the recovery ward PI: Principal investigator PMA: Postmenstrual age (see appendix one) PVL: Peri ventricular leukomalacia RA: Regional anaesthesia RCH: Royal Children's Hospital, Melbourne ROP: Retinopathy of prematurity SAE: Serious adverse events SAR: Serious adverse reaction SUSAR: Suspected unexpected serious adverse events TSC: Trial steering committee UTI: Urinary tract infection WPPSI-III: Wechsler preschool and primary scale of intelligence- Third Edition

SYNOPSIS

Title: A multi-site RCT comparing regional and general anaesthesia for effects on neurodevelopmental outcome and apnoea in infants

Chief investigators: [name] (PI), [name](PI), [name], [name], [name], [name], [name], [name], [name]

Objectives: The primary objective of this trial is to determine whether different types of anaesthesia [regional versus general] given to infants undergoing inguinal hernia repair result in equivalent neurodevelopmental outcomes. Secondary objectives are to describe the frequency and characteristics of apnoea in the post-operative period after both regional and general anaesthesia for inguinal hernia repair in infants, and determine the factors associated with apnoea.

Study population: 660 infants of postmenstrual age 60 weeks age or less, scheduled for inguinal hernia repair under anaesthesia. Exclusion criteria include recognised risk factors for adverse neurodevelopmental outcome or previous exposure to general anaesthesia. Infants born at less than 26 weeks gestation will be excluded.

1.1.1 Study acronym: *The GAS study*

1.2 Agents to be investigated: This trial will compare outcome in infants receiving a): general anaesthesia with the volatile general anaesthetic sevoflurane plus regional nerve blockade with the local anaesthetic bupivacaine or levobupivacaine, or b): awake regional anaesthesia using regional nerve blockade with bupivacaine or levobupivacaine alone.

1.3 Population to be studied: 660 infants of postmenstrual age 60 weeks or less scheduled for hernia repair.

1.4 Rationale

Recent animal data has provided evidence to suggest that several commonly used anaesthetic agents (including volatile anaesthetic agents) may be neurotoxic to the developing brain [1].

1.4.1 Anaesthesia in infancy

Anaesthesia in infants and neonates is becoming increasingly common. In 2002 in Western Australia 7.8% of male and 3.2% of female children aged less than 1 year had anaesthesia [2]. Of these infants 10% of the males and 20% of the females had the anaesthesia during their first 28 days of life. The use of anaesthesia in infants (and indeed in the foetus) is likely to further increase as more surgical options are available, as there is a greater appreciation of the ethical and developmental need for anaesthesia to reduce nociceptive stimuli, and as advances in anaesthesia practice reduce the short-term morbidity and mortality.

General anaesthesia in infants and neonates usually involves a volatile anaesthetic (e.g. sevoflurane, isoflurane or halothane) or an intravenous anaesthetic (e.g. barbiturate or propofol). These act via the GABA receptor. Anaesthesia may also be provided with awake regional nerve blockade using a local anaesthetic agent (for example spinal anaesthesia).

1.4.2 Apoptosis and neurodevelopment

Several studies have consistently demonstrated that neonatal rats, mice and guinea pigs exposed to GABA agonists, such as volatile anaesthetics, or to NMDA antagonists such as ketamine, have widespread neuronal apoptotic lesions and delays in achieving some developmental goals [3-7]. In rats the injury is most obvious when they are exposed to anaesthesia during the period of synaptogenesis at the age of 7 days. Recently neurotoxicity has also been demonstrated in prenatal rhesus monkeys exposed to ketamine [8].

The ontogeny of NMDA and GABA receptors is consistent with the existence of a period of potential neuro-toxicity mediated by anaesthetics. The composition of neonatal NMDA receptor subunits differs compared with adults [9], and the GABA receptor is excitatory rather than inhibitory in the neonatal brain [10].

Correlation of the stages of animal neural development with that of human brain development is imprecise. In the rat the period of synaptogenesis lasts from day 4 to day 10 and peaks at day 7. In the human this equates to the period from approximately the third trimester to one year of age. Thus, in theory humans may be susceptible to anaesthesia toxicity anywhere from ante-partum to late infancy.

Interspecies variation limits the generalisation of the animal data to humans. Similarly experimental conditions for rodents may be significantly different to conditions experienced by neonates undergoing surgery and anaesthesia. Differences include, concurrent oxygen, nutrition or blood glucose management, the dose of the agents used, the different organisation and plasticity of the human brain [1, 11, 12]. Compared with the time of exposure to anaesthesia, the developmental period is considerably longer in a human compared to a rat, however from a molecular biological perspective, apoptosis could be triggered irrespective of the usual period of neurodevelopment. Due to greater plasticity it is possible that the human brain is capable of accommodating greater apoptotic injury than the rat brain without any clinically significant effect to neurological development, although the evidence for this premise is limited.

Due to the difficulties with cohort data, the best way to provide convincing evidence for the safety of volatile anaesthesia is with a prospective randomised trial. Fortuitously, in many sites, anaesthesia is provided to infants undergoing inguinal hernia repair via one of two methods – general anaesthesia (GA) or regional anaesthesia (RA). RA can be with spinal or caudal anaesthesia or a combination of both. RA can be provided without exposure to any of the agents purported to be associated with neuro-toxicity. Inguinal hernia repair is one of the most common procedures to be performed in infancy and provides a large population of infants having similar surgery. The reasons for choosing RA or GA may depend on the age of the child, the experience of the surgeon or anaesthetist, and the perceived risk of apnoea. As outlined below the risks of apnoea after modern anaesthesia are not clearly defined. The presence of equipoise in choice of anaesthesia for a single, relatively common procedure provides an ideal setting for a prospective randomised trial. The most important potentially confounding variable is the influence of prematurity on developmental outcome and choice of anaesthesia. This potentially confounding variable makes stratified randomisation and a subsequent stratified analysis essential.

1.4.3 Apnoea

Neonates, particularly those born pre-term, normally have periods of irregular breathing (periodic breathing), but in some circumstances the pauses may be longer and may be described as apnoea. Apnoea in neonates is more common in the first 12 hours after anaesthesia [17] and the risk of post-anaesthesia apnoea is greater in neonates who were born pre-term [18, 19]. The exact significance of post-anaesthesia apnoea is unknown; the probable incidence of death or permanent injury due to post-anaesthesia apnoea being very low. It is assumed that there is a spectrum of severity and consequence.

Comparing general and spinal anaesthesia, three small trials have reported a reduced risk of apnoea in high risk babies receiving spinal anaesthesia [17, 20, 21]. These studies are difficult to interpret due to small numbers, different ways of measuring

apnoea and different general anaesthesia agents used [22]. A recent Cochrane review has called for a large well designed randomised trial to address this issue [23].

New general anaesthesia volatile agents such as sevoflurane and desflurane could, in theory, lower the risk of apnoea due to their faster elimination from the body [24]. However, one recent study has demonstrated that like the older agents, the new agent sevoflurane is still associated with a higher incidence of post-operative apnoea than spinal anaesthesia [25]. Also, like earlier studies the clinical relevance of this study is uncertain without a clear understanding of what is a "significant" episode of apnoea [26].

There is clearly a need for larger trials to evaluate the efficacy of apnoea prevention strategies in neonatal anaesthesia, including the use of RA. This study will provide useful data on the frequency and clinical significance of post-operative apnoea using RA and GA with modern anaesthesia techniques.

1.4.4 Success rate and complication rate of general and regional anaesthesia

Regional anaesthesia has varying popularity. Proponents for regional anaesthesia claim that it results in a fast recovery, early feeding and low respiratory complication rate. Detractors of regional anaesthesia cite a substantial failure rate with regional anaesthesia (up to 25%) and potential for distress in the child as the block is performed. However, data supporting these comments are sparse and contradictory. This study will enable the collection of good quality data to help in answering these questions.

1.4.5 Impact

If volatile anaesthesia *is* associated with poor neurodevelopmental outcome, reducing exposure to volatile anaesthesia will have a substantial impact on the community. Although surgery in infants is often unavoidable, and withholding anaesthesia is not an option, there are alternatives to volatile anaesthesia such as purely opioid-based anaesthesia using newer agents such as remifentanil or increased use of regional local anaesthesia.

There is already considerable public and parental concern regarding the toxicity of drugs to the foetus and the newborn. Avoiding *potentially* neurotoxic drugs or environmental agents during pregnancy has become a standard of care in our society. It is not surprising that a parent's concern continues after birth.

Previously the anaesthesia community has reassured the public that anaesthesia poses no specific toxic risk to neonates, however the recent animal data suggests such a reassurance cannot now be made without qualification. Resolving this issue, or at least being better able to inform the parents with better evidence-based data, should be a priority. This study will provide convincing evidence of any risk of clinically relevant neurotoxicity after exposure to brief anaesthesia in infants.

With respect to apnoea, current guidelines are based on little evidence [22]. Neonates are often routinely kept in hospital for observation after surgery. This is costly in

terms of limited hospital resources and disruption to families. A better understanding of apnoea would have obvious and considerable cost and safety benefit.

1.4.6 References:

- 1. Davidson, A. and S. Soriano, *Does anaesthesia harm the developing brainevidence or speculation?* Paediatr Anaesth, 2004. **14**(3): p. 199-200.
- 2. Sims, C., B. Stanley, and E. Milnes, *The frequency of and indications for general anaesthesia in children in Western Australia 2002-2003*. Anaesth Intensive Care, 2005. **33**(5): p. 623-8.
- 3. Young, C., et al., *Potential of ketamine and midazolam, individually or in combination, to induce apoptotic neurodegeneration in the infant mouse brain.* Br J Pharmacol, 2005. **146**(2): p. 189-97.
- 4. Jevtovic-Todorovic, V., et al., *Early exposure to common anesthetic agents causes widespread neurodegeneration in the developing rat brain and persistent learning deficits.* J Neurosci, 2003. **23**(3): p. 876-82.

1.5 Compliance

The trial will be conducted in compliance with the protocol, Good Clinical Practice (Therapeutic Goods administration, Australia) and all applicable regulatory requirements. The trial will be registered with the NH&MRC Australian Clinical Trials Registry and The National Library of Medicine (USA).

In the UK the trial will be conducted in compliance with the protocol, MRC GCP, Medicines for Human Use (Clinical Trials) Regulations 2004 as amended from time to time and the Research Governance Framework for Health and Social Care (2nd edition, April 2005)/ Community Care (2nd edition 2006), Data Protection Act, the Declaration of Helsinki and all relevant guidelines and legislation governing clinical research.

2. OBJECTIVES

2.1 Primary Aim

The primary aim of this prospective, observer blind, randomised, multi-site, controlled, clinical, equivalence trial is to determine whether different types of anaesthesia [regional vs general] given to infants undergoing inguinal hernia repair result in equivalent neurodevelopmental outcomes at 5 years of age (corrected).

2.3 Hypotheses

2.3.1 Primary Hypothesis: The WPPSI-III Full Scale IQ score at 5 years corrected age in infants who are anaesthetised for hernia repair is equivalent when using general anaesthetic compared with regional anaesthetic.

2.3.2 Secondary Hypothesis: Cognitive component of the Bayley III scale of infant development measured at 2 years of age in infants who are anaesthetised for hernia repair is equivalent when using general anaesthetic compared with regional anaesthetic.

3. STUDY DESIGN

3.1 Experimental Design: Prospective, observer blind, multi-site, randomised, controlled, equivalence trial

3.2 Randomisation: Randomisation to either of the two treatment groups (GA or RA) will be by block and stratified by site and gestational age at birth. Gestational age at birth strata will be:

- 26 weeks to 29 weeks and 6 days
- 30 weeks to 36 weeks and 6 days
- 37 weeks and more

Access to randomisation numbers will be via a 24 hour web-based randomisation service set up and maintained by A/[name] at The Data Management & Analysis Centre, Department of Public Health, University of Adelaide, South Australia: http://www.dmac.adelaide.edu.au/gasRandomisation

Entry to the website is password protected.

3.3 Blinding: The anaesthetist will be aware of the group allocation. The psychologist and paediatrician performing the 2 and 5 year neurodevelopmental assessments will be blinded to study group. Parents will not be told which group their child was in but they will be allowed to discover the group and will be told if asked. Parents will be clearly instructed that if they do discover the group then they should not inform the assessing psychologist. A record will be made of whether or not the parents or the psychologist became aware of the allocation. The apnoea assessment and recovery assessment will not be blinded.

3.4 Study duration: The duration of subject participation is five years.

- Children will be enrolled before surgery.
- Data will be collected before and during anaesthesia and in the early postoperative period.
- Formal neurodevelopmental assessment will occur at 2 and 5 years corrected age (see appendix 1 for definition of corrected age).

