4.4 Enrolment

Potential participants will be identified from theatre bookings or direct contact from surgeons or anaesthetists. After identification investigators will:

- Check medical history to confirm all inclusion criteria are met and no exclusion criteria are met.
- Confirm from both surgeon and anaesthetist that participant may be suitable and seek their approval to approach the family.
- Explain the project to the child's family and obtain written consent.

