4.5.3 Cancellation of surgery

If the surgery is cancelled after randomisation and not rescheduled, or cancelled and rescheduled greater than 48 hours after randomisation, then the reason for cancellation must be noted and the case is treated as a protocol violation. The child is not replaced. If the child has a hernia repair after 48 hours, the child should receive anaesthesia at the anaesthetist's discretion. Anaesthetic, apnoea and recovery data may be collected if possible. Note that as per other violations, the child should receive two and five year developmental assessment as per protocol. If the child receives surgery for hernia repair 48 hours or more after initial randomisation then they cannot be randomised again in the trial for that later surgery.

Note surgery may be *delayed for up to 48 hours* and the child retains their position in the study with same study group and study number (provided they continue to meet inclusion criteria).

If before anaesthesia and after randomisation a decision is made by surgeon or anaesthetist that the child is no longer suitable for the study for whatever reason (apart from cancelled surgery or withdrawn consent) and the child does not receive their allocated anaesthesia protocol, then the case should be treated as a protocol violation and data collected as possible. The child should receive the same post-anaesthesia apnoea data collection and developmental follow-up as per protocol. Note that if treating staff consider that it is in the child's best interests they always have the opportunity to not follow the protocol, but only the parents can withdraw the child completely from the trial.

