5.2.3 Experience of doctor performing nerve block

An essential component of the trial is a high success rate for regional anaesthesia. At each site awake spinal and caudal may be performed only by anaesthetists with an established high rate of success for the block (>90%). This anaesthetist may be called just to provide the block for the treating anaesthetist.

5.2.4 Asepsis: An aseptic technique is required for all blocks. This includes:

- Hands washed and sterile gloves worn
- Surgical masks to be worn
- Skin preparation with an antiseptic
- Area covered with sterile drapes

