8. STATISTICAL CONSIDERATIONS

8.1 Analysis of primary outcome

Since this an equivalence study, the primary outcome will be analysed on a perprotocol analysis basis to ensure a conservative estimate in the direction of nonequivalence. The means will be adjusted for gestational age at birth. The adjusted mean difference in Full Scale IQ Score between arms will be presented with a 2-sided 95% confidence interval. Equivalence will be accepted if the confidence interval of the difference in means lies within -5 and +5 points.

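### Staff who know the arm may judge a child no longer suitable after allocation but before anaesthesia, and the per-protocol primary analysis would presumably drop that child

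*Protocol*

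**What the plan says.** Before consent (Protocol 4.4), investigators check the history against all inclusion and exclusion criteria, and they also "Confirm from both surgeon and anaesthetist that participant may be suitable and seek their approval to approach the family". The exclusions in 4.3 cover a contraindication to either general or spinal/caudal anaesthesia. Section 11 adds that both treating clinicians must be comfortable with randomisation.

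On timing, 3.4 says "Children will be enrolled before surgery". Section 4.5.3 allows surgery to be delayed by up to 48 hours after randomisation with the same group kept, as long as the child still meets the inclusion criteria. On blinding, 3.3 says "The anaesthetist will be aware of the group allocation".

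Section 4.5.3 then covers a change of mind: "If before anaesthesia and after randomisation a decision is made by surgeon or anaesthetist that the child is no longer suitable for the study". Apart from cancelled surgery and withdrawn consent, it does not restrict the reason. If "the child does not receive their allocated anaesthesia protocol, then the case should be treated as a protocol violation and data collected as possible". Treating staff keep wide freedom, since "they always have the opportunity to not follow the protocol, but only the parents can withdraw the child completely from the trial". Apnoea data collection and developmental follow-up continue.

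Section 5.2.3 restricts awake spinal and caudal blocks to operators with a success rate above 90%. Section 8.1 states that "the primary outcome will be analysed on a perprotocol analysis basis" and calls this conservative. The only loss allowed for in 8.3 is 10% loss to follow-up.

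**The concern.** Randomisation makes the arms comparable only if the children analysed in each arm are not chosen with knowledge of the arm. Here a suitability decision can be taken after the arm is known and before anaesthesia starts, and its consequence is a protocol violation. In a trial decided on the per-protocol set, that is a way out of the deciding analysis.

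The reasons for leaving are unlikely to be neutral. Section 1.4.2 says the choice of technique may depend on the child's age, the clinicians' experience and the perceived risk of apnoea. Section 1.4.3 links apnoea to preterm birth, and 8.3 links preterm birth to lower IQ. Adjusting for three broad gestation strata removes differences between strata but not selection within a stratum. The practical pressure may also differ by arm, because only the awake regional arm needs an operator qualified under 5.2.3 and no step confirms that one is available before the draw.

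The claim in 8.1 that per protocol is conservative does not cover this route. Selective removal can widen or narrow the observed difference.

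**Working it through.** **Inputs.** From 8.1 and 8.3: margin 5, SD 15, one-sided alpha 0.025, true difference 1, power 90%, 598 infants needed, 660 enrolled, 10% loss. Assumed, because the protocol gives neither: *f*, the share of one arm that leaves the per-protocol set before anaesthesia, and *d*, how many points lower those children would score than the ones kept in the same arm at the same gestation.

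**Plan's own figure.** Two one-sided tests, normal approximation: power = Φ((5−δ)/SE − 1.96) + Φ((5+δ)/SE − 1.96) − 1, with SE = 15·√(1/n₁ + 1/n₂).
- 299 per arm, δ = 1: SE = 1.227, power 90.2%.
- With the noncentral t, 299 per arm gives 90.07% and 298 gives 89.97%, so 598 is reproduced exactly.
- Starting point for the illustration: 660 × 0.9 = 594, or 297 per arm; power 90.0%.

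**Shift.** Full-arm mean = (1−f)·kept + f·(kept − d) = kept − f·d. The per-protocol mean of that arm is therefore too high by b = f·d. The affected arm has n₂ = 297·(1−f).

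| f | d | b | SE | Power at δ = 1, numbers lost only | False equivalence at true 5, shift towards zero | Power at true 1, shift away from zero |
|---|---|---|---|---|---|---|
| 5% | 5 | 0.25 | 1.247 | 89.2% | 3.9% | 85.1% |
| 5% | 10 | 0.50 | 1.247 | 89.2% | 5.9% | 80.1% |
| 10% | 5 | 0.50 | 1.265 | 88.3% | 5.9% | 79.0% |
| 10% | 10 | 1.00 | 1.265 | 88.3% | 12.1% | 66.0% |

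Worked line for f = 10%, d = 10: n₂ = 267.3 and SE = 15·√(1/297 + 1/267.3) = 1.265.
- Towards zero, a true 5 is seen as 4: Φ(1/1.265 − 1.96) = Φ(−1.17) = 12.1%; the other side is met almost surely.
- Away from zero, a true 1 is seen as 2: Φ(3/1.265 − 1.96) = Φ(0.41) = 66.0%.

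**The last two columns are alternatives.** Which one applies depends on the arm that loses children and on the sign of the true difference.
- Lower-scoring children leave the regional arm and general anaesthesia is truly worse: the gap widens. Power falls as in the last column, while false equivalence at a true 5 drops below 2.5%, to 1.5%, 0.9% and 0.3% for shifts of 0.25, 0.5 and 1.0.
- Lower-scoring children leave the general arm and general anaesthesia is truly worse: the gap narrows. False equivalence rises as in the sixth column, and power does not suffer.
- If regional is truly worse, the two cases swap.

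**The case against.** The strongest reply is that the protocol already does most of what is needed. All criteria are confirmed before the family is approached, a contraindication to either technique excludes the child, and both clinicians must accept randomisation. Randomisation is tied to surgery by the 48-hour rule. Section 4.5.3 is a handling rule for a child whose position changes after entry. It protects clinical judgement, keeps the child in follow-up and lets only the parents withdraw the child. A qualified operator can be called in just for the block (5.2.3). The per-protocol set is not defined in the protocol, so exclusion is inferred. The share removed and the score gap are assumed. The failure rate of up to 25% in 1.4.4 does not supply the share, because it concerns failed blocks, which 5.7 handles separately.

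Most of this stands, and it rules out several stronger readings that a reader might infer:
- That allocation concealment fails at entry. The documents show no such failure; the issue is selection into the analysis set after randomisation.
- That the only check before randomisation is a provisional one. Sections 4.3, 4.4 and 11 say otherwise.
- That an unblinded anaesthetist is itself a fault. It is unavoidable.
- That the bias favours equivalence, or that false equivalence and power loss occur together. For a given true direction only one applies.

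What the reply does not answer is timing. None of these checks has to be repeated when the allocation is drawn, and the later decision is open-ended and made with the arm known. The moment at which the anaesthetist learns the arm is not stated, but nothing prevents it from coming before that decision.

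**Conclusion.** The point holds as a weakness in the order of steps, and it is worth a cheap correction. The unblinded anaesthetist, the interval of up to 48 hours, the open-ended suitability decision, the violation status and the per-protocol primary analysis are all in the text. That these children leave the per-protocol set is an inference from the last two; the statistical analysis plan, not available here, may define the set differently. It could not change when the allocation is drawn.

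The size cannot be derived from the protocol. Under the illustrative 5–10% and 5–10 points, the shift is at most one fifth of the margin (1.0 of 5), but it is not negligible for the error rates. The loss of numbers alone matters little: power falls from 90.0% to 89.2% or 88.3%. The direction is open, so the conservative rationale in 8.1 cannot be relied on for these departures.

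**What to change.** 1. In 3.2 and 4.4, state that on the day of surgery the surgeon and anaesthetist reconfirm eligibility for either technique and that an operator qualified under 5.2.3 is available. The allocation is drawn only then, from the existing 24-hour web service, as the last step before anaesthesia. A child judged unsuitable before the draw is not randomised.
2. Keep the 4.5.3 route and full clinical discretion for anything that arises after the draw. Record the reason and report such cases by arm.
3. In 8.1, report an as-randomised analysis of the primary outcome beside the per-protocol one. It is feasible because 4.5.3 continues developmental follow-up of these children. If the two disagree, the counts by arm and reason will help to show why.

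The cost is protocol wording and a change in site workflow. Sites must be ready for either technique until shortly before the start, and a few children may not be enrolled when no qualified operator is available.

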3.7.2 Medical history at two years

Details of all hospital attendances and admissions to hospital after discharge following hernia repair. Exposure to any anaesthetic agents or benzodiazepines since discharge from hospital after hernia repair.

Details of any recurrence of hernia on either side since repair

3.7.3 Neurodevelopmental assessment at two years:

- Bayley Scales of Infant Development III (BSID-III): Cognitive, language and motor scales
- Paediatric assessment including neurological examination to determine presence of cerebral palsy
- Visual and hearing acuity tests
- Delayed Alternation and Spatial Reversal Tasks (Espy) [An experimental task]

It will be noted whether or not the parent or psychologists are aware of allocation.

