6.2.1 Other measures of neurodevelopmental outcome

6.2.1.1 Neurodevelopmental secondary outcomes at 2 years:

- Cognitive, motor and language scales of the Bayley Scales of Infant Development III [Bayley 2005].
- A paediatric assessment including a neurological examination to determine the presence of cerebral palsy will be conducted by a paediatrician blinded to the type of anaesthetic used.
- Data regarding visual and hearing acuity will be collected, or where not previously conducted, visual and audiology assessments will be arranged.
- Some sites will perform the experimental Delayed Alternation and Spatial Reversal tasks (Espy)

6.2.1.2 School age developmental outcome at 5 years:

- A paediatric assessment as per 2 years.
- General intellectual ability, verbal, visuo-spatial and processing speed skills are incorporated into the Wechsler Preschool and Primary Scale of Intelligence - Third Edition (WPPSI-III) The primary outcome is the full scale, while subscales will be computed as secondary outcomes.
- Auditory and visual attention will be assessed using the NEPSY tasks.
- The behaviour features of executive dysfunction will be assessed via the Behavioural Rating of Executive Function (BRIEF).

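### The paediatrician is declared a blinded assessor, but is left out of both the instruction to parents and the record of who learned the allocation

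*Protocol*

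**What the plan says.** Protocol section 3.3 (Blinding) names two blinded assessors: "The psychologist and paediatrician performing the 2 and 5 year neurodevelopmental assessments will be blinded to study group". Section 6.2.1.1 repeats this for the 2-year examination that looks for cerebral palsy, which "will be conducted by a paediatrician blinded to the type of anaesthetic used". Section 6.2.1.2 carries the same examination forward to 5 years: "A paediatric assessment as per 2 years".

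Section 3.3 also sets out what parents may know: "Parents will not be told which group their child was in but they will be allowed to discover the group and will be told if" they ask. Two safeguards follow:

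- An instruction: "Parents will be clearly instructed that if they do discover the group then they should not inform the assessing psychologist".
- A record: "A record will be made of whether or not the parents or the psychologist became aware of the allocation".

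The lists of assessment data for 2 years (3.7.3) and 5 years (3.8.3) each restate the record in the same terms: "It will be noted whether or not the parent or psychologists are aware of allocation".

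**The concern.** The protocol accepts that some parents will know the group, and it puts measures in place to stop that knowledge from reaching the assessor and to document it if it does. Both measures are written for the psychologist. A parent who follows the instruction to the letter may still tell the paediatrician, and no item listed in the protocol would show that this had happened.

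A neurological examination and a decision on whether cerebral palsy is present depend partly on clinical judgement. The trial rests on the possibility that general anaesthesia is neurotoxic (1.4, 1.4.2), so an examiner who knows the arm has a reason to expect a difference in one direction. These are listed secondary outcomes, and section 8.2.1 reports frequency data as a between-group difference with a 95% confidence interval. For these outcomes the observer-blind description of the design would rest on a declaration, without the supporting measures the psychologist has.

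The point belongs in the protocol rather than in an analysis plan. If awareness is not noted at the visit, it cannot be reliably recovered at analysis.

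**Working it through.** No formula applies; the check is a comparison of the provisions.

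| Provision | Section | Psychologist | Paediatrician | Parents |
|---|---|---|---|---|
| Declared blinded at 2 and 5 years | 3.3 | yes | yes | no (may discover, told on request) |
| Blinding restated for the examination | 6.2.1.1 | – | yes | – |
| Parents told to withhold the group from | 3.3 | yes | not named | – |
| Awareness recorded, general rule | 3.3 | yes | not named | yes |
| Awareness recorded at 2 years | 3.7.3 | yes | not named | yes |
| Awareness recorded at 5 years | 3.8.3 | yes | not named | yes |

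1. *Could psychologist be meant to include the paediatrician?* No. Section 3.3 lists the two side by side as separate assessors, and Appendix II lists their labour costs separately.

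2. *Is the gap closed elsewhere?* No. No section tells parents to withhold the group from the paediatrician, and none records whether the paediatrician became aware. The sentence in section 9 that keeps chief investigators blinded concerns access to data, not the examiner at the visit.

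3. *Which outcomes are exposed?* Those from the paediatric assessment at both ages. The WPPSI-III Full Scale IQ (primary, 6.1) and the Bayley-III cognitive score (secondary hypothesis, 2.3.2) are psychological tests. Section 10 says WPPSI-III examiners will typically have psychological training, and the awareness items in 3.7.3 and 3.8.3 name psychologists. Given that, both safeguards cover those tests.

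4. *How large could it be?* Enrolment is 660. With the 10% loss to follow-up allowed in section 8.3, 660 × 0.90 = 594 children would be examined. Let K be the share of examined children whose parents know the group. Disclosure by parents can unblind between 0 and K × 594 paediatric examinations at an age with that follow-up. The protocol gives no value for K, but parental awareness is to be recorded, so K will be known from the data. The number within that range where the paediatrician was actually told will not be. Disclosure from any other source falls outside this bound and is not recorded at all.

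5. *What check remains?* The paediatric outcomes can be compared among children whose parents stayed unaware. This removes the parental route. It also discards examinations that stayed blinded although the parents knew, and it misses disclosure from other sources. It is a usable proxy, but not a direct record.

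**The case against.** The strongest reply is that the paediatrician's blinding is stated twice, parents are not told the group by default, and parental awareness is recorded at both ages. On this view the blinding has some protection, and the comparison restricted to unaware parents tests the very route at issue. All of this stands. A reader might infer from the omissions that the paediatric blinding is wholly unprotected and uncheckable, or that only the psychologist's awareness is recorded. The documents support neither. What holds is that, of the two assessors, only the psychologist's awareness is recorded, and that the remaining check is indirect.

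A reader might also infer that some examinations will in fact be done unblinded, because the history taken at follow-up must bring up the anaesthetic. The text does not establish this. The 2-year history (3.7.2) asks about anaesthetic exposure after discharge from the hernia repair, not about the allocated anaesthetic. The 5-year history (3.8.2) lists no anaesthetic item. The protocol does not say who takes the history or in what order. Disclosure is plausible, not certain, and the protocol gives no basis for prescribing a visit order.

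Finally, the equivalence conclusion is unaffected: the exposed outcomes are secondary and section 8.2.1 sets no margin for their frequency comparison. That limits the importance of the point. It does not remove the mismatch between the declared blinding and the measures meant to support it.

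**Conclusion.** The point holds as an inconsistency of limited scope. The paediatrician is a declared blinded assessor but is missing from the one instruction to parents and from all three statements of the awareness record. Unblinding of the paediatric assessment at 2 and 5 years is therefore not specifically guarded against or directly recorded.

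The amount of unblinding cannot be estimated from the protocol, and it may be none. Bias in the neurological examination and cerebral palsy results is possible but not shown. The conclusion that the primary WPPSI-III outcome and the Bayley-III are unaffected assumes that psychologists administer both, which the protocol implies but does not state outright. The correction is worth making because it is nearly free and the missing information is hard to recover after the visits.

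**What to change.** - In section 3.3, extend the instruction so that parents who learn the group are asked not to inform the assessing psychologist *or paediatrician*.
- In sections 3.3, 3.7.3 and 3.8.3, record the paediatrician's awareness of allocation as its own item, separate from that of the parent and of the psychologist.

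The cost is one phrase in the parent instruction and one tick box on each of the two visit forms. It needs no extra staff, and the sample size and the analysis of the primary outcome do not change. With the item in place, the paediatric outcomes can be checked directly among examinations where the paediatrician was unaware.
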